8.2. Inclusion Criteria

- Participant is willing and able to give informed consent for participation in the study.
- Male or Female, aged 18 years or above.
- Under the care of the cardiovascular clinic at OUH Owning or having access to a smartphone with either Android or iOS
- Being able to use a smartphone app
- Being able to walk

A subgroup of 15 patients will be identified among those who are more willing to use the app to perform the additional measurements with the trundle wheel and to answer the questionnaire. This group should include a balanced representation of age groups and sexes.

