6. OBJECTIVES AND OUTCOME MEASURES

The population to be studied is composed of hospital outpatients who have conditions where the 6MWT is routinely used in clinical care, and/or are using the 6APP as an alternative.

The objective is: To evaluate the usefulness of adopting remote, mobile-based 6MWT among hospital outpatients, within the constraints imposed by the SARS-COV2 pandemic.

Objectives	Outcome Measures	Timepoint(s) of evaluation of this outcome measure (if applicable)
Primary Objective To assess whether patients are able and willing to use a smartphone app for the 6MWT	Percentage of participants who perform at least one app-based 6MWT before patient consultation.	At 3, 6, 9 and 12 months after the start of the study.
Secondary Objectives To assess the accuracy of the app-based measurement. To assess whether differences in distance walked according to the app altered management of patients.	Comparison of walked distance (6MWD) measured by the app versus a trundle wheel reference. Number of clinical investigations and multidisciplinary team discussion triggered by variations in app-based 6MWD.	12 months. At 3, 6, 9 and 12 months after the start of the study.

To assess the usability and acceptance of the app.	Standard usability and acceptance questionnaires, semi-structured interviews.	12 months.
To collect raw data from phones' sensors to allow the development of future algorithms for app-guided 6MWT.	Localisation position (GPS), speed, acceleration, step count, gyroscope samples collected during 6MWT.	12 months.
To determine whether the use of the 6MWT reduces time spent and number in hospital visits.	Time spent in hospital attendances and number of hospital visits made during use of the 6MWT compared with previous periods.	12 months.
To compare the use of 6MWT during pandemic with pre-pandemic use.	Total number of 6MWTS performed during 2020 pandemic period compared with pre-pandemic period.	12 months.

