8. PARTICIPANT IDENTIFICATION

8.1. Trial Participants

All patients under the care of the cardiovascular clinics in Oxford, who are able to walk and use a smartphone.

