8.3. Exclusion Criteria

The participant may not enter the study if ANY of the following apply:

- Long term oxygen therapy
- Cognitive impairments
- Cannot use a smartphone
- Pregnancy
- Not able to complete a 6MW

- Any other significant disease or disorder which, in the opinion of the Investigator, may either put the participants at risk because of participation in the trial, or may influence the result of the trial, or the participant's ability to participate in the trial.

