9.2. Screening and Eligibility Assessment

Patients will be screened every week according to the scheduled clinic phone calls or visits. A list of candidates who match inclusion and exclusion criteria (except use of smartphone) will be prepared before consultation.

During the consultation, patients will be asked about their access and fluency with smartphones to further verify compliance with the criteria.

The subgroup of 15 patients will be chosen among those using the app depending on the frequency of their use of the app and general willingness to participate in the study.

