12.2. Sample Size Estimation

For part 1, we will not use sampling as we aim to involve all patients in the cardiovascular clinics who require a 6MWT and are able to use the app.

With regards to part 2, our 15 patients cohort is in agreement with typical usability studies.

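### The primary percentage covers only consenting, smartphone-capable participants, so it cannot show how many outpatients smartphone access or ability rules out; the non-use interviews exclude never-users

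*Combined protocol and SAP*

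**What the plan says.** **Objective and population.** Section 6 gives the primary objective as "To assess whether patients are able and willing to use a smartphone app for the 6MWT". It opens with "The population to be studied is composed of hospital outpatients who have conditions where the 6MWT is routinely used in clinical care" and adds, as an and/or alternative, patients already using the app in place of the clinic test. Neither limb sets a smartphone requirement for the population as a whole.

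**Entry.** Section 8.2 requires consent, access to a smartphone and "Being able to use a smartphone app". Section 8.3 excludes anyone who "Cannot use a smartphone". The limit is stated openly: section 8.1 describes participants as "All patients under the care of the cardiovascular clinics in Oxford, who are able to walk and use a smartphone", and section 12.2 says "we aim to involve all patients in the cardiovascular clinics who require a 6MWT and are able to use the app".

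**Outcome and analysis.** The outcome is a percentage of participants with at least one app test. Section 12.1 computes it for recruited patients, counting tests from the time they confirm the download. Section 12.3 gives the analysis population as all participants.

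**Screening and logging.** Section 9.2 (Screening) states: "A list of candidates who match inclusion and exclusion criteria (except use of smartphone) will be prepared before consultation". Smartphone access and fluency are then checked at the consultation. The event codes in section 9.3 (Subsequent Visits) cover consent, refusal, withdrawal, installation, declared faults and shared app tests. No code covers smartphone ineligibility.

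**Interviews.** Section 9.3, Part 2, says that the interviews should explain why patients do or do not use the app. Section 7 places questionnaire and interviews in the 15-patient subgroup. Section 9.2 (Screening) says these patients "will be chosen among those using the app depending on the frequency of their use of the app", section 8.2 picks them for greater willingness to use it, and section 9.3 for ability and engagement.

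**The concern.** A patient who cannot use a smartphone, or who declines the study, never enters the denominator and so cannot lower the percentage. Part of the ability that the objective asks about is settled at the door. A high percentage could be reported as showing that outpatients can and will do the test by app, when it describes those already screened as capable and consenting. A clinic planning a remote service also needs to know how many of its patients would be left out.

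The second problem concerns explanation. A low or moderate percentage would prompt the question of why some consented patients did not test. The interviews meant to answer it would hold no one who never used the app, and the usability and acceptance results would describe engaged users.

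**Working it through.** **1. Where each kind of patient goes under the plan**

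- Otherwise eligible, no smartphone or unable to use one: on the pre-consultation list, then excluded. No code; not in the percentage.
- Able, declines: RECRUIT-DENY with reason; not in the percentage. Later app use is not logged.
- Agrees by telephone, consent form never posted back: no code.
- Consents, never installs: recruited, so in the percentage. No code or step asks why.
- Consents, installs, declares a fault: in the percentage, coded APP-ISSUE.
- Consents, installs, no fault, no test: in the percentage. No code or step asks why.
- Consents and shares a test no more than two weeks old: APP-6MWT.

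Section 12.1 reports neither the list nor the refusals.

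**2. Possible size of the gap**

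There is no plan figure to reproduce. The synopsis gives 250 to 500 patients without a target rate or precision, and section 12.2 says that Part 1 is not sampled. All rates below are assumed.

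Let *a* be the share of listed patients able to use a smartphone and *p* the percentage among recruited patients. If able refusers use the app as participants do, and unable patients do not use it, uptake over the list is *a × p* and the gap is *p × (1 − a)*.

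- *a* = 0.9: *p* = 0.3, 0.5, 0.7, 0.9 gives 3, 5, 7, 9 points.
- *a* = 0.7: the same *p* gives 9, 15, 21, 27 points.

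Three scenarios with *p* = installed × tested:

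- 0.95 × 0.8 = 0.76; with *a* = 0.9, list uptake 0.684, gap 7.6 points.
- 0.85 × 0.8 = 0.68; with *a* = 0.7, list uptake 0.476, gap 20.4 points.
- 0.80 × 0.8 = 0.64; with *a* = 0.6, list uptake 0.384, gap 25.6 points.

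Pairing lower ability with lower uptake is itself an assumption.

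The figure that can be observed, testers over listed, is *a × c × p*, where *c* is the consenting share of able patients. At *p* = 0.80 it is 0.95 × 0.90 × 0.80 = 0.684, 0.80 × 0.70 × 0.80 = 0.448, or 0.60 × 0.50 × 0.80 = 0.240. It counts every refuser as a non-user, so it is a lower bound.

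For scale, the 95% half-width 1.96 × √(p(1 − p)/n) at *p* = 0.5 is 6.2 points (n = 250) and 4.4 points (n = 500); at *p* = 0.8 it is 5.0 and 3.5. A gap of 20 points exceeds sampling error. A gap of 3 points (*a* = 0.9, *p* = 0.3) does not, since the half-width there is 5.7 or 4.0.

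**3. Never-installers**

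Because counting starts at confirmed download, an analyst could drop patients who never confirm it. With 60% uptake among all recruited, the percentage would then read 0.60/0.90 = 67%, 0.60/0.80 = 75% or 0.60/0.70 = 86% at assumed download shares of 90%, 80% or 70%.

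**4. Non-testers and the interviews**

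Consented patients without a test number *n × (1 − p)*. At *p* = 0.76, 0.68, 0.64 this is 60, 80, 90 for n = 250 and 120, 160, 180 for n = 500. Some will have used the app but shared no recent test, so this is not a count of never-users. Never-users have no place in a group drawn from users.

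If 3 or 4 of the interviewees were non-testers chosen at random, a reason held by a share *s* of non-testers would be heard at least once with probability 1 − (1 − s)^k. For *s* = 0.5 this is 0.875 or 0.938; for *s* = 0.3 it is 0.657 or 0.760.

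**The case against.** The strongest defence is that the restriction is declared. The outcome is a percentage of participants, sections 8.1 and 12.2 define them as smartphone-capable, and uptake among people who can use the device is a legitimate feasibility question. This stands against any charge of hidden selection. It does not make the percentage answer an objective worded for patients at large.

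A reader might infer that the percentage says nothing about ability. The documents do not support that. Entry screens for general smartphone ability, while the outcome also needs this app downloaded, a test completed outdoors and a recent result shared. A capable participant can fail at any of these steps.

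A reader might also infer that refusal of the study is unwillingness to use the app. Sections 5.4 and 9.1 (Recruitment) show the clinics recommending the app, and some patients using it, regardless of the study. Leaving refusers out is therefore not clearly an error in measuring willingness.

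Finally, a reader might infer that non-users are never asked why. Reasons for refusal and withdrawal are logged, faults have a code, every row has a comments field, EXTRA-OBS takes free observations, and clinicians ask about recent app tests at each contact. The gap is narrower: patients who stay in the study, report no fault, and do not install or test. It is also true that section 9.3 does not itself say where the 5 to 10 interviewees come from; section 7 does.

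**Conclusion.** The point holds as a mismatch between objective and denominator, not as an undisclosed restriction or an invalid outcome. The percentage is informative about completing an app test among consenting, smartphone-capable participants. It is silent on how many otherwise eligible outpatients are ruled out by smartphone access or ability. Most of that information arises during screening but is not reported and, for smartphone ineligibility, not coded. The interview aim and the interview sample also do not fit each other.

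The size is unknown. The 3 to 27 point range rests on assumed ability of 70% or 90%, assumed uptake of 30% to 90%, and able refusers behaving like participants. The gap would be larger if refusers use the app less, and this cannot be estimated because their use is not logged. None of these figures is evidence that true uptake is lower by a given amount. The changes are worth making because they cost little and the screening counts may not be recoverable later.

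**What to change.** **(1) Denominator and reporting.** Keep the primary percentage over all recruited patients and state that never-installers count as non-performers. Word the conclusion for consenting, smartphone-capable patients. Add an event code for smartphone ineligibility and a record of unreturned consent forms. Beside the primary result, report aggregate counts de-duplicated by patient: listed; no smartphone or cannot use the app; declined or form not returned; enrolled; installed; at least one app test. Present the last count over the listed total as a lower bound on uptake. For patients who did not consent, keep to counts as far as approvals allow, and leave their rows out of the file sent to Malmo unless that is approved.

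**(2) Interviews.** Select some of the 5 to 10 interviewees from consented Part 1 participants with no APP-6MWT entry, with the needed consent and voice-recording authorisation. If this is not done, limit the usability, acceptance and interview conclusions to engaged users. Extending the online questionnaire to all Part 1 participants is optional; it widens the study and would bring some non-response.

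**Cost.** A few codes, counts from a list already planned, the same number of interviews, an amendment to the information sheet and consent form, and a check that counts on non-consenting patients fit the approvals. The drawback is a less favourable companion figure that is only a lower bound.

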8.3. Exclusion Criteria

The participant may not enter the study if ANY of the following apply:

- Long term oxygen therapy
- Cognitive impairments
- Cannot use a smartphone
- Pregnancy
- Not able to complete a 6MW

- Any other significant disease or disorder which, in the opinion of the Investigator, may either put the participants at risk because of participation in the trial, or may influence the result of the trial, or the participant's ability to participate in the trial.

9. TRIAL PROCEDURES

9.1. Recruitment

Outpatients undergoing follow up in the cardiovascular outpatient clinics in Oxford will be eligible for participation. Some of these patients are already using the app, regardless of the study, for example in the case of the pulmonary hypertension clinic. They will be approached by a member of the clinical team for consideration and recruited during a regular consultation either via phone call or during a visit in the clinic. They will be asked to download the app over the Internet.

9.2. Screening and Eligibility Assessment

Patients will be screened every week according to the scheduled clinic phone calls or visits. A list of candidates who match inclusion and exclusion criteria (except use of smartphone) will be prepared before consultation.

During the consultation, patients will be asked about their access and fluency with smartphones to further verify compliance with the criteria.

The subgroup of 15 patients will be chosen among those using the app depending on the frequency of their use of the app and general willingness to participate in the study.

9.3. Informed Consent

Patients to be recruited will be sent a study information sheet and consent form by post before being recruited. The information sheet will explain how to download and use the app and will introduce the study. Informed consent forms will have to be signed and sent by post (a pre-stamped folder will be prepared). For those patients attending the clinic physically, the information sheet and the informed consent will be given and signed during the day of the clinic.

Signed informed consents will be collected by the research team, either on the day of their appointment or if a tele-medicine appointment, it will be sent back to the research team. If any patient denies consent or withdraws, the reason will be recorded on the spreadsheet.

The subgroup of 15 patients selected for part 2 of the study will be sent an additional leaflet with instructions and further consent will be sought with a different consent form.

The participant must personally sign and date the latest approved version of the Informed Consent form before any trial specific procedures are performed.

Written and verbal versions of the Participant Information and Informed Consent will be presented to the participants detailing no less than: the exact nature of the trial; what it will involve for the participant; the implications and constraints of the protocol; the known side effects and any risks involved in taking part. It will be clearly stated that the participant is free to withdraw from the trial at any time for any reason without prejudice to future care, without affecting their legal rights and with no obligation to give the reason for withdrawal.

The participant will be allowed as much time as wished to consider the information, and the opportunity to question the Investigator, their GP or other independent parties to decide whether they will participate in the trial. Written Informed Consent will then be obtained by means of participant dated signature and dated signature of the person who presented and obtained the Informed Consent. This consent will be obtained at the time of either their clinic appointment, either face to face or by telephone and the consent form returned by post. The person who obtained the consent must be suitably qualified and experienced, and have been authorised to do so by the Chief/Principal Investigator. A copy of the signed Informed Consent will be given to the participant. The original signed form will be retained at the trial site, and a copy to be filed in medical records.

9.1. Enrolment

All eligible patients will be enrolled from outpatient clinics. They will be recruited to the trial and not randomised .

9.2. Baseline Assessments

There is no baseline assessment of each patient, however, we will request baseline statistics about 6MWT performed during 5 years previous to the pandemic. These data will be pulled from the electronic health record. Only the patient ID and the date of the 6MWT are needed for this analysis.

9.3. Subsequent Visits

Part 1: logging events

At each consultation, either through phone or face to face visit, the clinician who contacts the patient will log on the spreadsheet the distance walked and a series of study-related events, marked with a code. Coding is needed to simplify and automate later analysis. The following is an example of the structure of the spreadsheet:

Patient number	hospital	Date	Event	Comments

Events codes are explained in the following table:

Event	Code	Example comments
The patient accepts to join the study and provides consent.	RECRUIT-ACCEPT	Patient has accepted to join the study.
The patient denies consent and does not join the study.	RECRUIT-DENY	Patient denies consent because of lack of time.
The patient has decided to withdraw from the study.	RECRUIT-WITHDRAW	Patient's conditions have worsened and she cannot walk 6 minutes any more.
The patient declares to have the app installed on a phone he/she can use.	APP-OK	Patient has downloaded the app, everything works as expected.
The patient declares that he/she is having technical issues with the app.	APP-ISSUE	The app crashes when started on iPhone 11.
The patient shares a 6MWT not older than 2 weeks either through email or by telephone.	APP-6MWT	Date: 3/5/2021, distance: 420 m
The patient needs further evaluation because of changed medical conditions. The role of the app-based 6MWT is also coded depending on whether it was irrelevant to the decision, partially involved or fundamental for the decision. The event is logged once per decision (further contacts with the patient resulting from the decision should not include the tag).	NEW-EVAL-NO-6MWT NEW-EVAL-PART-6MWT NEW-EVAL-FULL-6MWT	The patient shows a general deterioration, last 6MWT was below 300m. An MDT is required.
The patient needs a change in the treatment. The role of the app-based 6MWT is specified as above.	NEW-TREAT-NO-6MWT NEW-TREAT-PART-6MWT NEW-TREAT-FULL-6MWT	Medication regime increased because of a lower 6MWD in the last 4 weeks.

Regular clinic 6MWT	CLINIC-6MWT	Date: 23/4/2021, distance: 450m
Additional observations	EXTRA-OBS	Because of reduced risk of corona infection, patient is invited to the clinic.

A list of possible codes with their explanation will be included in a tab of the spreadsheet.

Part 2: accuracy, usability and acceptance assessment

Fifteen patients will be selected based on their ability and engagement and invited to perform 10 additional 6MWT using the app and a trundle wheel simultaneously. An additional informed consent form will be sent to these patients. To those who accept, the research team will send a pre-packaged trundle wheel.

At the end of each of these tests, patients will need to share the raw data collected by the phone during the test through the app's "share" button. When prompted, users will choose to share the data through email and send them to a special address that will be set up for the purpose in Malmö. The app will automatically attach to these emails the data it used to compute the distance including the patient's geographical position (longitude, latitude, altitude, speed) and inertial sensors data (acceleration, inclination, detected steps). Patients will be instructed to also add the distance measured by the trundle wheel to the message for reference.

In order to study the accuracy under different conditions, patients will be instructed to perform 5 tests walking along paths the shape of which is known to obtain the best distance estimation (straight or gently curved paths). Patients will also perform 5 more tests walking over paths that may be more "challenging" for the app, for example those including narrow curves, U-turns or in confined spaces.

If less than 15 trundle wheels are purchased for the study, patients will be asked to send the meters back to the clinical centre once the 10 tests are completed. Trundle wheels will be then cleaned and disinfected and sent to another batch of patients until covering 15 subjects.

Towards the end of the study, patients of the subgroup will be sent an online questionnaire related to usability and acceptance to be filled in electronically. The questionnaire will be based on the validated and widely used uMARS questionnaire¹² and the Mobile Health Technology Acceptance Model (MoHTAM) questionnaire¹³.

Five to ten patients will be selected for an additional phone-based short interview. Notes from the interview will be taken and voice will be recorded if technically possible. The interview will aim at

¹² <https://mhealth.jmir.org/2016/2/e72/>

¹³ <https://ieeexplore.ieee.org/abstract/document/6149947>

understanding causes and motivations for use or non-use of the app, based on a technology acceptance model. Patients will have to sign an authorization to allow the registration of their voice. This will be sent together with the informed consent.

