12. STATISTICS

12.1. Description of Statistical Methods

The analysis of the data involves reviewing the spreadsheet. The use of the labels will simplify analysis and will avoid manual coding. The R programming environment will be used to compute statistics.

To assess whether patients are able and willing to use a smartphone app for the 6MWT.

For each recruited patient, we will compute the number of app-based 6MWT results available since they confirmed that they have downloaded the app. From this number, we will compute a histogram of the number of available app-based 6MWT per patient and the percentage of participants who perform at least one app-based 6MWT prior to every consultation.

To assess the accuracy of the app-based measurement.

We will compare the walked distance measured by the app with the distance measured by the trundle wheel for those tests that provide both information. We will compute descriptive statistics (mean, standard deviation, percentiles) of the difference and BlandAltman plots.

To assess whether differences in distance walked according to the app altered management of patients.

We will use the codes related to clinical evaluations to compute descriptive statistics about the frequency of those evaluations and about how many of them were triggered by observed changes of the 6MWD.

To assess the usability and acceptance of the app.

We will compute descriptive statistics of the results of the usability and acceptance questionnaires. We will use thematic content analysis to analyse the interview transcripts.

To collect raw data from phones' sensors to allow the development of future algorithms for app-guided 6MWT.

We will also use the sensors data sent from patients involved in part 2 of the study to identify strategies to improve the algorithm that computes the distance. The availability of this type of data would be unique and would open interesting research in computer science and biomedical engineering. The University of Malmo is planning to experiment signal processing (Kalman filters, FIR filters) and machine learning (LSTM RNN) techniques to improve the accuracy of the current GPS-based algorithm and to explore the possibility to develop an indoor version of the algorithm based purely on the inertial sensors (acceleration).

To determine whether the use of the 6MWT reduces time spent and number in hospital visits.

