14. QUALITY ASSURANCE PROCEDURES

Data produced on the electronic health record will be analysed every 3 months to assess their quality by the research team. Assessment will focus on the presence of the keywords, their correct spelling and the consistency of the data.

Upon suspicion of the app not being able to produce accurate data, or of misuse of the app, the clinical team may request patients to share the details of a test. These data can then be used on a web tool to visualise the path walked, altitude and statistics that may help the clinician to identify the problem. The web tool retains the data locally in the browser and does not share them with any server or third party over the Internet.

The study may be monitored, or audited in accordance with the current approved protocol, GCP, relevant regulations and standard operating procedures.

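### The Part 1 log has no required row for each consultation and no code for a missing app test, so the share of participants tested before every consultation cannot be reliably computed from it

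*Combined protocol and SAP*

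**What the plan says.** Section 6 (and the synopsis) gives the primary outcome as "Percentage of participants who perform at least one app-based 6MWT before patient consultation", evaluated at 3, 6, 9 and 12 months. Section 12.1 analyses the same objective as "the percentage of participants who perform at least one app-based 6MWT prior to every consultation". Its data source is the Part 1 log: "The analysis of the data involves reviewing the spreadsheet".

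The log is described under 9.3 Subsequent Visits. At each consultation, by phone or face to face, "the clinician who contacts the patient will log on the spreadsheet the distance walked and a series of study-related events, marked with a code". The columns are patient number, hospital, date, event and comments, introduced with "The following is an example of the structure of the spreadsheet". The code for an app test, APP-6MWT, applies when "The patient shares a 6MWT not older than 2 weeks either through email or by telephone". The other codes cover recruitment, consent refusal and withdrawal, app installed or faulty, new evaluations, treatment changes, clinic walk tests and additional observations.

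Section 14 provides a 3-monthly quality check: "Assessment will focus on the presence of the keywords, their correct spelling and the consistency of the data". Under 9.2 Screening and Eligibility Assessment, "Patients will be screened every week according to the scheduled clinic phone calls or visits"; that schedule is used there to find candidates.

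**The concern.** A percentage tested before every consultation needs two facts for each participant: which consultations took place, and whether a recent app test was available at each. The log records the second fact only when the answer is yes, and has no entry dedicated to the first. A quiet consultation with no test and no decision matches no required code and has no distance to enter. In the data it looks the same as a consultation that never happened or one the clinician forgot to log.

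If the analyst takes the logged dates as the list of consultations, the denominator is selected on the outcome: a consultation with a test leaves a row, and one without may not. Missing rows then count in favour of uptake.

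The reason for a missing test is also at stake. The primary objective asks whether patients are able and willing to use the app. Section 17.1 has participants complete a self-assessment checklist and not walk if they fail it. That is different from unwillingness, but the log need not distinguish the two.

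**Working it through.** **Step 1. Code list against the analysis.** The documents give no expected uptake, number of consultations per patient or precision target, so there is no stated figure to reproduce. The check starts from what a row can show.

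| Situation at a consultation | Row required by the code list? |
|---|---|
| App test shared | Yes, APP-6MWT |
| No app test, but another codable event (app fault, clinic walk test, new evaluation, treatment change) | Yes, under that other code |
| No app test and nothing else to report | No; APP-OK or EXTRA-OBS could be used, but nothing requires it |
| No consultation held | No |

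The last two lines cannot be told apart. The section 12.1 measure depends on telling them apart.

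**Step 2. Other sources in the plan.** The weekly schedule in 9.2 serves screening. Section 12.1 also plans a count of hospital visits, but for a different objective, and it does not mention phone consultations. Neither is linked to the uptake analysis. Under section 13.1 the spreadsheet goes to Malmo for analysis, with no mention of a clinic list going with it.

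**Step 3. Size, by illustration.** All inputs are assumptions: *k* independent consultations per patient; *p*, the chance of an app test before each; *t*, the chance that a no-test consultation still leaves some other dated row; and logged rows treated as all consultations. All recruited patients stay in the denominator, because section 12.1 starts from each recruited patient.

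- True share tested before every consultation: *p*^*k*
- Chance that a consultation leaves no row: *u* = (1 − *p*)(1 − *t*)
- Share the log would show (at least one APP-6MWT row and no logged consultation without one): (*p* + *u*)^*k* − *u*^*k*
- Per-consultation uptake the log would show: *p* / (*p* + (1 − *p*)*t*)

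With *p* = 0.70 and *k* = 3, the true share is 0.70³ = 0.343, and true per-consultation uptake is 0.70.

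| *t* | *u* | Log, every consultation | Log, per consultation |
|---|---|---|---|
| 0.2 | 0.24 | 0.94³ − 0.24³ = 0.817 | 0.70/0.76 = 0.921 |
| 0.3 | 0.21 | 0.91³ − 0.21³ = 0.744 | 0.70/0.79 = 0.886 |
| 0.6 | 0.12 | 0.82³ − 0.12³ = 0.550 | 0.70/0.88 = 0.795 |
| 1.0 | 0 | 0.70³ = 0.343 | 0.70/1.00 = 0.700 |

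Other values give the same direction. At *t* = 0.3, *p* = 0.9 with *k* = 4 gives 88.5% against a true 65.6%; *p* = 0.5 with *k* = 2 gives 60.0% against a true 25.0%.

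**Step 4. The other reading of the outcome.** The share with at least one test at any time is 1 − (1 − *p*)^*k*. For *p* = 0.70 and *k* = 3 this is 1 − 0.027 = 0.973. It does not contain *t*, so missing no-test rows do not change it.

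**The case against.** A reader might infer that uptake is overstated however the primary outcome is defined. The documents do not support that. Section 6 can be read as at least one test per participant. The denominator then comes from RECRUIT-ACCEPT rows and the numerator from any APP-6MWT row; a patient who never shares a test still counts in the denominator. This part of the objection stands. One gap remains on that reading: at the 3, 6 and 9 month evaluations, a recruited patient with no consultation yet since joining cannot be told apart from one who attended without a test.

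A reader might also infer that every no-test consultation vanishes. That goes too far. Logging is called for at each consultation, several codes can leave a dated row without an app test, and the column layout is only an example. The gap is confined to otherwise uneventful consultations, and the documents do not say how common these are.

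Nor do the documents show that the 3-monthly check could never notice a gap. It includes presence of keywords and consistency of data. But it names no list of expected consultations to compare against, so finding missing rows is not part of the plan. Consultation dates might be recovered later from clinic schedules. No section plans this, and test status and the reason for no test may not be recoverable.

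Finally, it is tempting to extend the point to the frequency of clinical evaluations in section 12.1. That does not follow. Section 6 defines that outcome as a number, and section 12.1 asks how many evaluations were triggered by a change in distance, for which the denominator is evaluations.

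**Conclusion.** The point holds for the measure written in section 12.1 and for any per-consultation uptake. Neither can be computed reliably from the spreadsheet, and if logged rows stand in for consultations the bias is upward. It does not hold for the share of recruited patients with at least one test.

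The size cannot be derived from the documents. Under the illustration, a true 34% would appear as about 82%, 74% or 55% when 20%, 30% or 60% of no-test consultations leave another row, with no bias when all do. These figures assume independent consultations and an analyst who counts only logged rows, which the plan does not state. The matter is more than missing detail because it has to be settled while data are being collected.

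**What to change.** In 9.3 Subsequent Visits, require one dated row for each consultation held with each enrolled participant, by phone or in clinic. Each such row carries either APP-6MWT or a new code, APP-6MWT-NONE, with a short list of reasons that includes failing the self-assessment checklist in section 17.1. Other event codes continue as now.

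In section 14, add to the 3-monthly check a reconciliation of these rows with the scheduled-clinic list already used for screening, separating consultations that were held from those that were not.

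In section 12.1, state that consultation-based percentages are computed from these rows.

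The cost is one new code, reuse of an existing list and a few seconds per consultation. Reported uptake may be lower than the current log would have shown.
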